4. LIST OF ACRONYMS/ABBREVIATIONS AND DEFINITIONS OF TERMS

4.1. List of Acronyms/Abbreviations

ADL	Activities of daily living
AE	Adverse event
AESI	Adverse event of special interest
ALT	Alanine aminotransferase
ASA	American Society of Anesthesiology
AST	Aspartate aminotransferase
AUC	Area under the curve
BMI	Body mass index
CAS	Color Analog Scale
CFR	Code of Federal Regulations
CK	Creatine kinase
СРК	Creatine phosphokinase
CRF	Case Report Form
CTCAE	Common Terminology Criteria for Adverse Events
DSMB	Data Safety Monitoring Board
ECG	Electrocardiogram
eCRF	Electronic case report form
ER	Emergency room
FDA	Food and Drug Administration
GCP	Good Clinical Practice
GGT	Gamma-glutamyl transpeptidase
ICF	Informed consent form
ICH	International Conference on Harmonisation
IEC	Independent Ethics Committee
IND	Investigational New Drug
IRB	Institutional Review Board
JCAHO	Joint Commission on Accreditation of Healthcare Organizations
LDH	Lactate dehydrogenase
NCI	National Cancer Institute
NDA	New Drug Application
NRS-R	Numeric rating scale – at rest
NSAID	Non-steroidal anti-inflammatory drug

OR	Operating room
PACU	Post-anesthesia care unit
PCA	Patient-controlled analgesia
РК	Pharmacokinetic
PMR	Post Marketing Requirement
PPD	Premier Perspective TM Database
PTAE	Pre-treatment adverse event
SAE	Serious adverse event
SAP	Statistical analysis plan
SD	Standard Deviation
TIBC	Total iron binding capacity
TEAE	Treatment-emergent adverse event
UIBC	Unsaturated iron binding capacity
US	United States
WHO	World Health Organization

4.2. Definition of Terms

Pharmacokinetic terms are defined in Section 12.2.

5. ETHICS

5.1. Institutional Review Board/Independent ethics committee

Prior to enrolling subjects into this study, each study site will obtain the approval of an Institutional Review Board (IRB)/Independent Ethics Committee (IEC) that complies with the International Conference on Harmonisation (ICH) Good Clinical Practices (GCP) and/or the United States (US) Food and Drug Administration (FDA) Title 21 Code of Federal Regulations (CFR) Part 56. Attention is directed to the basic elements that are required to be incorporated into the informed consent form (ICF) under 21 CFR Part 50.25 and ICH GCP.

5.2. Ethical Conduct of the Study

This study will be conducted in accordance with the clinical research guidelines established by the FDA Title 21 CFR, Parts 50 (including Subpart D regarding additional safeguards for children in clinical investigations), 54, 56, and 312, and the ICH GCP. Study documents will be maintained in accordance with applicable regulations.

5.3. Subject Information, Consent, and Assent

Before a subject undergoes any study-specific screening procedures, the investigator or designee will thoroughly explain to the subject's parent/guardian the purpose of the study, the associated procedures, and any expected effects and potential adverse reactions. A copy of the IRB- or IEC-approved ICF will be provided to the subject's parent/guardian, who will be given sufficient time and opportunity to inquire about the details of the study and decide whether or not to enroll their child. The subject's parent/guardian, and the study staff with whom he or she discusses the ICF, will sign and date the ICF. If the subject is capable of providing assent, he or she will be provided with an explanation of the study and an IRB- or IEC-approved written assent form to read. Once the investigator is assured that the subject understands the concepts involved, the subject will be asked to give assent (if applicable) to participate in the study. The subject's parent/guardian must sign the ICF and the subject must give assent (if applicable) before any study-specific procedures are performed. A copy of the fully signed ICF will be given to the parent/guardian and a copy of the assent form (if applicable) will be given to the subject.

The investigator will explain to the subject's parent/guardian that they are completely free to decline entering their child into the study and to withdraw their child from the study at any time, for any reason, without risking his or her medical care. The subject may also independently withdraw assent to participate in the study. Similarly, the investigator and/or Pacira Pharmaceuticals, Inc. (Pacira) will be free to withdraw the subject at any time for safety or administrative reasons. Any other requirements necessary for the protection of the human rights of the subject will also be explained, according to the current ICH GCP (E6) and the Declaration of Helsinki (1964, and as amended through 2013).

6. INVESTIGATORS AND STUDY ADMINISTRATION STRUCTURE

Information regarding the investigators, sites, laboratories, and other service providers is available upon request to the IRB/IECs and regulatory agencies.

7. INTRODUCTION

With the identification of acute pain by the World Health Organization (WHO) as a problem of global proportions (Gureje 1998) and the publication of the Joint Commission on Accreditation of Healthcare Organizations (JCAHO) pain standards, there is increasing acceptance of pain as the fifth vital sign, on par with blood pressure, pulse, temperature, and respiration rate (Lynch 2001).

Postsurgical pain is one of the most common forms of acute pain (Schug 1993; Carr 1999). In contrast to chronic pain, for which no adaptive value has been demonstrated, acute pain is the normal physiological response to tissue insult or injury and has adaptive value by serving as a warning of danger or damage. Most acute pain is either treatable or avoidable, especially when it occurs in a clinical setting. However, if acute pain is poorly or inappropriately treated, it may progress to chronic pain (Perkins 2000; Petersen-Felix 2002). Thus, effectively modulating the response to acute pain may be considered a primary step in the prevention of chronic pain (Stephen 2003). The suboptimal management of acute pain has been recognized as a problem by clinicians for more than 50 years (Papper 1952; Marks 1973) and has been formally identified as a public health concern by various societies and government institutions worldwide.

In 1992, the US Agency for Health Care Policy and Research developed guidelines for the management of postoperative pain in the hopes of increasing awareness of the consequences of poor pain control in the postoperative setting and promoting better pain management techniques (Stephen 2003). These consequences, which include delayed healing, longer hospitalization, and the development of chronic pain, are significant not only from the patient's perspective (decrease in functionality and quality of life) but also from the health economic perspective (increase in healthcare resource utilization and costs).

Each year, more than 5 million children undergo surgery in the US, and it is estimated that up to 75% of these patients experience significant postoperative pain and receive postoperative analgesia (Owen 1990). Opioid use is ubiquitous among hospitalized patients undergoing surgical procedures (Kessler 2013). One consequence is a growing epidemic of opioid use, misuse, and diversion (Morris 2015; Joranson 2006). Specific to the pediatric population, prescription opioid use before the 12th grade is a predictor of future opioid misuse, with a 33% increase in future risk of misuse after high school (Miech 2015).

A multimodal approach to postoperative analgesia, using a combination of agents (e.g., opioids, local anesthetics, non-steroidal anti-inflammatory drugs [NSAIDs]), and delivery techniques (patient-controlled analgesia [PCA], epidural and regional blocks) is currently recognized as

best practice for pain management (Breivik 1995a; Breivik 1995b; American Society of Anesthesiologists [ASA] Task Force 1995; Dahl 2000). EXPAREL[®] was developed to extend pain relief with a single-dose administration without the use of indwelling catheters and to decrease the requirement for supplemental opioid medications.

A New Drug Application (NDA) for EXPAREL was submitted as a 505(b)(2) application and subsequently approved by the US FDA on October 28, 2011 (NDA 022-496). As part of the approval for EXPAREL, Pacira is required to conduct pediatric studies as a Post Marketing Requirement (PMR).

7.1. Indication

EXPAREL was initially approved by the US FDA in 2011 for single-dose administration into the surgical site to produce postsurgical analgesia. The indication was amended and approved by the US FDA in 2018 to read: "EXPAREL is indicated for single-dose infiltration in adults to produce postsurgical local analgesia and as an interscalene brachial plexus block to produce postsurgical regional analgesia. Safety and efficacy have not been established in other nerve blocks."

EXPAREL was developed to provide a prolonged period of decreased pain and decreased opioid use with a single-dose administration without the use of indwelling catheters.

Effective postsurgical pain control is a critical element in patient recovery following surgery, as the majority of patients may experience significant pain, particularly in the first few days. Improved postsurgical pain management contributes to better healing, faster patient mobilization, shortened hospital stays, and reduced healthcare costs (ASA Task Force 1995).

7.2. Current Therapies/Treatments

Current modalities of postsurgical analgesic treatment include infiltration and nerve block with local anesthetic agents, usually combined with the systemic administration of analgesics (multimodal therapy). Multimodal therapy usually includes opioid medications, NSAIDs, and/or acetaminophen provided through a variety of routes including intravenous, transdermal patch, and oral administration. Opioids are widely used and considered amongst the most powerful analgesics; however, they also have considerable drawbacks, including time and resources required for monitoring opioid-related side effects. A reduction in the use of postoperative opioids is desirable to decrease the incidence and severity of opioid-induced adverse effects, such as respiratory depression, nausea, vomiting, constipation, somnolence, pruritus, and urinary retention.

With over 70 million surgeries performed annually in the US, postoperative pain is a ubiquitous condition among the US population. While it is a predictable component of the postoperative process, such pain is often poorly managed, resulting in clinical and physiological changes that increase morbidity and mortality (inability to ambulate early, etc.), diminish quality of life, and extend length of stay, thereby increasing hospital expenditures (Oderda 2007) and reducing

patient satisfaction. Effective relief of acute pain with minimal opioid complications, on the other hand, may improve clinical outcomes, avoid complications (like delay in regaining bowel function or an inability to tolerate liquid and solid oral intake), and conserve healthcare resources. As such, the JCAHO requires that all healthcare facilities practice adequate pain management and monitor opioid-related adverse events (AEs) (Apfelbaum 2003).

Opioid analgesics have long been established to be the most effective agents used for the management of moderate to severe postoperative pain, and are currently considered the mainstay of treatment. However, AEs related to opioid administration (e.g., nausea, vomiting, ileus, confusion) represent one important reason to develop opioid-sparing strategies. Indeed, fear of gastrointestinal side effects, such as nausea and vomiting, as well as respiratory depression, present major limitations for the widespread use of opioid analgesics (Chernin 2001 and Viscusi 2009). Furthermore, management of opioid-related events often requires medical attention (e.g., opioid antagonists, antiemetic agents) and increased pharmacy/nursing time, which may raise healthcare expenses (Carroll 1994).

7.3. EXPAREL (bupivacaine liposome injectable suspension)

Bupivacaine is one of the longer-acting local anesthetics, but even so it has a limited duration of action after local administration, usually less than 8 hours. EXPAREL is a bupivacaine liposome injectable suspension. It consists of microscopic spherical, multivesicular liposomes (DepoFoam[®] drug delivery system), organized in a honeycomb-like structure comprising numerous non-concentric internal aqueous chambers containing a bupivacaine base at a concentration of 13.3 mg/mL. Each chamber is separated from adjacent chambers by lipid membranes. The lipids (phospholipids, cholesterol, and triglycerides) are naturally occurring or close analogs of endogenous lipids. Bupivacaine is slowly released from the DepoFoam particles by a complex mechanism involving reorganization of the barrier lipid membranes and subsequent diffusion of the drug over an extended period of time. EXPAREL has been noted in infiltration studies to have a bimodal curve (Apseloff 2013), with an initial peak occurring at approximately 0 to 2 hours and a second peak at approximately 24 to 48 hours (Hu 2013).

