11. TREATMENTS

11.1. Treatments to be Administered

Study Drug

Dosing of EXPAREL for this study will be based on body weight, with a starting dose of 4 mg/kg. This weight-based dosing applies to Part 1 and Part 2 of the study.

The study drug will be administered prior to wound closure. The investigator must document the size of the incision. Each infiltration site should be spaced 1.0 to 1.5 cm apart and approximately 1 to 1.5 mL should be delivered into both deep and superficial areas. Following infiltration, the tissue should visibly expand with minimal leakage.

All eligible subjects will receive a single dose of EXPAREL intraoperatively at the end of surgery via local infiltration into the surgical site. EXPAREL can be administered as is or may be expanded with normal (0.9%) saline to increase the volume up to a final concentration of 0.89 mg/mL (i.e., 1:14 dilution by volume). The total volume of expansion will be dependent on the incision length. Details regarding the expansion of EXPAREL are provided in the Study Drug Infiltration Guide.

Total Volume of Expansion

The investigator must document the total volume used for each surgery.

• EXPAREL 4 mg/kg + normal saline (20–60 mL based on the incision size) = total volume.

For example: If the infiltration sites are 1.5 cm apart, then a 10 cm incision would be 10×2 sides $\times 3$ layers = 60 cm. If there is 1 mL infiltrated every 1.5 cm, the total volume would be 40 mL.

In Part 1, all eligible subjects will receive a single dose of EXPAREL intraoperatively at the end of surgery via local infiltration. EXPAREL can be administered as is or expanded to increase volume up to a final concentration of 0.89 mg/mL (i.e., 1:14 dilution by volume) with normal

saline (0.9% sodium chloride solution). The total volume of expansion will be dependent on the size of the wound.

In Part 2, all eligible subjects randomized to EXPAREL will receive a single dose of EXPAREL intraoperatively at the end of surgery via local infiltration. Dosing will be informed by the results of Part 1 and any recommendations based on the complete safety review.

Subjects randomized to the active control group will receive bupivacaine HCl 2 mg/kg, with a maximum dose of 175 mg.

Postsurgical Pain Management

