11.3. Identity of Investigational Products

11.3.1. Description of EXPAREL

EXPAREL is formulated as a sterile, non-pyrogenic, white to off-white, preservative-free, homogeneous suspension of bupivacaine encapsulated into multivesicular lipid-based particles (the DepoFoam drug delivery system).

Bupivacaine is present at a nominal concentration of 13.3 mg/mL. EXPAREL will be provided in 20 mL, 1.3% (13.3 mg/mL) single-use, clear glass vials.

EXPAREL vials should be stored refrigerated between 2°C and 8°C (36°F to 46°F).

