11.3.2. Description of Reference Product

The reference product will be bupivacaine HCl. All information on the drug administered, dose, frequency, and duration will be captured in the electronic case report form (eCRF).

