11.5. Selection of Doses in the Study

The dose of EXPAREL (4 mg/kg) was selected to provide similar exposure in pediatric subjects as was seen in adults. A Population PK model was developed using all data obtained from the infiltration studies in adult subjects (SKY0402-C-201, SKY0402-C-208, SKY0402-C-316, SKY0402-C-317, and SKY0402-C-401). Simulations from this model were performed to predict bupivacaine plasma concentrations in pediatric subjects aged 6 to less than 17 years. The dose of EXPAREL administered will not exceed 266 mg, regardless of the weight of the subject.

The selection of the 4 mg/kg dose is also supported by real world evidence collected at the Cleveland Clinic, where 375 pediatric patients have received EXPAREL at a mean dose of 4.1 ± 1.8 mg/kg, with no significant AEs attributed to EXPAREL use.

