3. STUDY OVERVIEW

This is a two-part study to evaluate the PK and safety of EXPAREL in pediatric subjects aged 6 to less than 17 years. Part 1 will evaluate the PK and safety in subjects aged 6 to less than 17 years, while Part 2 will assess the safety in subjects aged 6 to less than 17 years. This is also a two-group study. Group 1 will include subjects aged from 12 to <17 years old undergoing spine surgery. Group 2 will include subjects aged from 6 to <12 years old undergoing spine or cardiac surgery. (Table 1)

In Part 1, subject enrollment will be conducted in parallel to include the older age group (12 to <17 years old; Group 1) and the younger age group (6 to <12 years old; Group 2).

Subject enrollment for Part 2 (of each group) will commence upon completion of Part 1 (of that group). In Part 2, subject enrollment will be conducted in parallel to include the older age group (12 to <17 years old; Group 1) and the younger age group (6 to <12 years old; Group 2).

Dosing of EXPAREL will be based on body weight, with a starting dose of 4 mg/kg (maximum 266 mg). Dosing of Bupivacaine HCl will be based on body weight, with a starting dose of 2 mg/kg (maximum 175 mg).

	Part 1 (PK and Safety)	Part 2 (Safety)
Group 1: subjects aged 12 to <17 years	EXPAREL 4 mg/kg [N=15]; or	EXPAREL 4 mg/kg [N = 15]; or
(Surgery: Spine Surgery)	bupivacaine HCl 2 mg/kg [N =15]	bupivacaine HCl 2 mg/kg [N =15]
Group 2: subjects aged 6 to <12 years (Surgery: Spine or Cardiac Surgery)	EXPAREL 4 mg/kg [N=15]	EXPAREL 4 mg/kg [N =15]

Part 1 (Pharmacokinetics [PK]) - Subjects aged 6 to less than 17 years

Part 1 is a multicenter, randomized, open-label study in 45 subjects aged 6 to less than 17 years of age undergoing spine or cardiac surgeries. Part 1 is divided in 2 groups: Group 1 will include subjects aged 12 to less than 17 years of age, while Group 2 will include subjects aged 6 to less than 12 years of age.

Part 1, Group 1, is an active-controlled, open-labeled, PK evaluation study in subjects aged 12 to less than 17 years undergoing spine surgery. The active comparator will be bupivacaine HCl. The planned sample size for Part 1, Group 1 is 30 subjects (15 subjects per treatment group). Subjects will be randomized 1:1 to receive either a single dose of EXPAREL 4 mg/kg (maximum 266 mg) or bupivacaine HCl 2 mg/kg (not exceeding a maximum bupivacaine HCl dose of 175 mg total) intraoperatively at the end of surgery via local infiltration.

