- Apparent clearance (CL/F) will be estimated as Dose/AUC0-∞.
- Apparent volume of distribution (Vd/F) will be estimated based on the teriminal phase as Dose/($\lambda_z \cdot AUC0-\infty$).

In addition, a population PK modeling will be performed using all PK data collected during the study. The population PK analysis plan will be developed separately.

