6.7.3 Pharmacokinetic Concentrations and Variables

A complete data listing will be provided for all PK bupivacaine concentration data. Concentrations that are BLOQ will be indicated in the listing.

A plot of bupivacaine concentration-time data, with original scale and semi-log scale overlain on the same page will be created for each individual subject.

If different than the preceding plot, a plot of dose-normalized concentration-time data, with the original scale and semi-log scale overlaid on same page, will also be created for each individual subject.

Plasma bupivacaine concentrations for each formulation will be summarized at each nominal time window (any out-of-window results would be shown only in a listing). The following descriptive statistics

will be presented: n, geometric mean, arithmetic mean, SD, %CV, median, minimum and maximum. Results will be summarized by treatment group (EXPAREL or bupivacaine HCl) for Group 1 and by surgery type (cardiac or spine) for Group 2. Plots of mean bupivacaine concentration over time will be created with the original scale and semi-log scale overlain on the same page. If the number of subjects in a group is less or equal to 3, then individual concentration over time curves will be plotted instead of the mean concentration. For group 1, there will be two plots overlain for the two treatments. For group 2, there will be two separate plots for the two types of surgery.

Pharmacokinetics parameters will be presented in the data listings and descriptive summary statistics, including the arithmetic mean, median, minimum, maximum, standard deviation, %CV of mean, geometric mean, %CV of geometric mean. Differences will be compared between the two formulations using single factor ANOVA.

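### SAP 6.7.2 leaves the chemical form of Dose undefined: EXPAREL milligrams are bupivacaine base and comparator milligrams are the HCl salt, so CL/F and Vd/F as written are not on one scale

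*Protocol*

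**What the plan says.** **EXPAREL.** Protocol 7.3 describes the liposome chambers as "containing a bupivacaine base at a concentration of 13.3 mg/mL". Protocol 11.3.1 gives the presentation: "EXPAREL will be provided in 20 mL, 1.3% (13.3 mg/mL) single-use, clear glass vials". Protocol 11.5 sets the cap: "The dose of EXPAREL administered will not exceed 266 mg, regardless of the weight of the subject".

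**Comparator.** Protocol 11.3.2 states: "The reference product will be bupivacaine HCl". SAP 3 gives its dose and cap in the same terms: "bupivacaine HCl 2 mg/kg (not exceeding a maximum bupivacaine HCl dose of 175 mg total".

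**Calculation.** Under SAP 6.7.2 one assay measures bupivacaine in plasma, whichever product was given. On clearance it says "Apparent clearance (CL/F) will be estimated as Dose/AUC0", with the AUC extrapolated to infinity. Vd/F is Dose divided by the product of λz and the same AUC. Dose is not defined further.

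**Comparison.** SAP 6.7.3 says of the PK parameters: "Differences will be compared between the two formulations using single factor ANOVA". Mock Table 14.4-1.1 sets EXPAREL beside bupivacaine HCl with a p-value row, and its programmer note adds CL/F and Vd to the parameters shown. The same SAP section plans dose-normalised concentration plots for individual subjects, where these differ from the unnormalised plots.

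**The concern.** Plasma concentrations are bupivacaine in both arms, so AUC is on one scale. The doses in the numerator are not: one is stated as base, the other as a salt that weighs more than the base it contains. A programmer who enters the recorded milligrams into the stated formulas would divide base by AUC in one arm and salt by AUC in the other. The comparator's CL/F and Vd/F would then exceed EXPAREL's by a fixed factor that has nothing to do with how either product behaves, and the between-formulation comparison would show that factor as a formulation difference. The error is systematic, so more subjects would not remove it.

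**Working it through.** **1. Confirm the EXPAREL scale from the plan's own figures.**
- Vial volume × strength (Protocol 11.3.1): 20 mL × 13.3 mg/mL = 266.0 mg. This equals the cap in Protocol 11.5.
- Protocol 11.1 gives the greatest dilution as "final concentration of 0.89 mg/mL (i.e., 1:14 dilution by volume". One part in fifteen: 13.3 / 15 = 0.887 mg/mL, which agrees.

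Both figures use the strength that Protocol 7.3 describes as base, so the EXPAREL mg/kg dose and cap are in milligrams of base.

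**2. Effect of using the salt dose unconverted.** Let f be the weight fraction of base in the salt, f = MW(base) / MW(salt).
- CL/F from the salt dose = D / AUC; from the base dose = f·D / AUC; ratio = 1/f.
- Vd/F from the salt dose = D / (λz·AUC); from the base dose = f·D / (λz·AUC); ratio = 1/f.
- A concentration divided by the salt dose instead of the base dose is multiplied by f.
- AUC, Cmax, Tmax and half-life contain no dose term and do not change.

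**3. Size.** The documents give no molecular weights. Assumed: base 288.435 (C18H28N2O). Neither document says whether the comparator's labelled strength refers to the anhydrous salt or the monohydrate, so both are shown.

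| | Anhydrous HCl | HCl monohydrate |
|---|---|---|
| Assumed MW of salt | 324.896 | 342.911 |
| f = 288.435 / MW | 0.888 | 0.841 |
| 1/f (factor on CL/F and Vd/F) | 1.126 | 1.189 |
| Comparator CL/F and Vd/F too high by | 12.6% | 18.9% |
| 2 mg/kg salt as base (2 × f) | 1.78 mg/kg | 1.68 mg/kg |
| 175 mg cap as base (175 × f) | 155 mg | 147 mg |
| Nominal EXPAREL:comparator dose ratio, 4 / (2 × f) | 2.25 | 2.38 |
| Comparator dose-normalised concentration too low by (1 − f) | 11.2% | 15.9% |

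On the milligrams as printed, the nominal dose ratio is 4 / 2 = 2.00.

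**4. What this could do to the p-value.** Inputs: 15 per arm (Part 1, Group 1), two-sided 5% test, true CL/F equal on the base scale. The log scale and the CVs are assumptions, since the documents give neither. With two groups, the ANOVA in the text and the two-sided t-test in the table footnote are the same test if variances are taken as equal.
- σ = √ln(1 + CV²); noncentrality = ln(1/f) / (σ√(2/15)), with ln(1/f) = 0.119 to 0.173 and √(2/15) = 0.365.
- CV 30%: σ = 0.294, noncentrality 1.11 to 1.61; probability of a significant difference 0.19 to 0.34.
- CV 50%: σ = 0.472, noncentrality 0.69 to 1.00; probability 0.10 to 0.16.

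The nominal value is 0.05.

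**The case against.** - **The SAP does not rule out conversion.** It leaves Dose undefined, and the analyst may intend base equivalents. This stands. The plan shows an undefined term, and the bias follows only if the stated doses are used as they are.
- **This is not the primary PK analysis.** A reader might infer that the offset contaminates the trial's primary result. The documents do not support that. The primary objective concerns EXPAREL's own PK, and EXPAREL is already on the base scale. Protocol 12.2 takes its endpoints from the population model. Protocol 15.1 and 15.7 plan no hypothesis or significance testing, and SAP 6.11 declares the noncompartmental analysis an addition to the protocol. No stated study decision uses the p-value.
- **Dose-normalised concentrations are not compared formally.** They are individual-subject plots, produced conditionally, with no planned summary or test between arms. This stands; the mismatch matters there only if plots are read across arms.
- **CL/F and Vd/F differences already mix in F, and λz may not be estimable in everyone.** SAP 6.7.2 needs three points after Cmax. In the spine schedule only two planned samples follow sample 6, so a late EXPAREL peak can leave these parameters uncomputed. Fifteen per arm is therefore an upper limit, and fewer subjects would lower the probabilities in step 4. The 1/f factor on each computed comparator value is unchanged, and a known arithmetic offset should not be added to real differences in F.
- **The factor can be corrected later without new data.** True, but results and p-values already produced would have to be rerun.

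**Conclusion.** The point holds as an undefined Dose that, read literally, puts the two formulations on different scales. Comparator CL/F and Vd/F would be overstated relative to EXPAREL by about 12.6% to 18.9%. The direction is certain, because the salt weighs more than the base. The size rests on assumed molecular weights and on the unknown strength convention of the commercial HCl product. The false-difference probabilities rest further on assumed CVs and log-scale analysis, and serve only as illustration.

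The reach is limited to comparator CL/F and Vd/F in the SAP's additional between-formulation comparison, and to any dose-normalised plots read across arms. Comparisons within EXPAREL by age or surgery type are untouched. The population PK analysis plan is a separate document that cannot be judged here, though its dose input could carry the same mismatch. Nothing here says that any administered dose is wrong. The change is worth making because following the plan as written gives a wrong number and the correction costs almost nothing.

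**What to change.** Add to SAP 6.7.2: *For CL/F, Vd/F and any dose-normalised concentration, Dose is the administered amount expressed as mg of bupivacaine base for both products. The bupivacaine HCl dose is multiplied by the base fraction derived from the labelling of the product used.* State the factor, repeat it as a footnote to Table 14.4-1.1, and use the same dose scale in the population PK dataset.

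The cost is one sentence, one constant and one footnote. Protocol 11.3.2 already requires details of the reference drug given to be recorded in the eCRF, which should help identify the product. No dose, sample or visit changes. If left until outputs exist, comparator CL/F and Vd/F, their p-values and any affected plots would need to be rerun.
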